8.2 Vital signs

For each continuous vital sign parameter, descriptive summary statistics for values observed at Baseline and at each scheduled timepoint, and for the change from Baseline will be presented. For this summary, the Baseline is the last non-missing value prior to the start of Fentanyl treatment. This summary will be presented in the randomized safety population.

Vital sign data will be provided in a listing for subjects in Randomized Safety population.

8.3 Electrocardiogram (ECG)

For each continuous ECG parameter, descriptive summary statistics for values observed at Baseline and at each scheduled timepoint, and for the change from Baseline will be presented. For this summary, the Baseline is the last non-missing value prior to the start of Fentanyl treatment. This summary will be presented in the randomized safety population.

ECG data will be provided in a data listing for subjects in Randomized Safety population.

9 Pharmacodynamic Analysis (Part 2 Only)

9.1 Pharmacodynamics Over Time Profiles

The mean profile of smoothed data of MV and raw data of TCO₂ for each treatment (i.e., each pooled period) will be plotted with overlay of individual subject's replicated treatments. In addition, mean profiles for each treatment will be overlaid in one figure.

Individual and mean profiles will also be provided for change from baseline and % Change from Baseline based on the smoothed data of MV and raw data of TCO₂.

Minute Ventilation (MV): Individual time profiles of MV raw data are generally highly variable. To better characterize the magnitude and time course of opioid agonist/antagonist effects on ventilation, medians will be moved over a 4-minute centered window continuously to smooth the raw data. In the earlier [NAL1003](#) study, this 4-minute window was determined to be the shortest window that adequately reduced the moment-moment variation while accurately preserving time course differences.

To avoid any carryover effects from the previous drug, the smoothing algorithm will be applied in a piecewise fashion, as follows:

- Data before any fentanyl (without any opioid agonist) administration
- Data from beginning of fentanyl administration to antagonist administration (only the effect from fentanyl)
- Data on and after antagonist administration with continuing fentanyl administration (the effect of naloxone and any antagonist)

Transcutaneous CO₂: Individual time profiles of TCO₂ raw data will be used as is.

Parameters (Prior to Antagonist Administration Phase)

For MV and TCO₂, the following parameters will be calculated to evaluate the action of OIRD for each subject and each period, during the period of fentanyl only administration:

- Baseline (Pre-treatment value) - Median value of the PD data during the 10 minutes before the start of Fentanyl
- OIRD value - Median value of the PD data between -10 and -5 minutes before the start of the antagonist

9.2 Primary Endpoint(s) Analysis

Change in MV from opioid induced nadir (Opioid Induced Respiratory Depression (OIRD))

- Pre-specified Time Point: 5 min after administration of antagonist

The change in MV from OIRD at 5 min after administration of antagonist will be provided by treatment in tables and figures with 95% confidence interval presented.

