OOWS	Objective Opioid Withdrawal Scale
PaCO ₂	arterial partial pressure of carbon dioxide
PCO ₂	partial pressure of CO ₂ in mm Hg (transcutaneous CO ₂)
PD	pharmacodynamics(s)
pH	negative log of hydrogen ion concentration
PI	principal investigator
PK	pharmacokinetic(s)
PO ₂	Partial pressure of oxygen
PPLP	Purdue Pharma Limited Partnership
PT	preferred term(s)
RBC	red blood cell (count)
ROU	healthy recreational opioid users
RR	respiratory rate
RVM	respiratory volume monitor(ing)
SAP	Statistical Analysis Plan
SAS	Statistical Analysis System
SC	subcutaneous
SGOT	serum glutamic-oxaloacetic transaminase (also AST)
SGPT	serum glutamate pyruvate transaminase (also ALT)
SoA	Schedule of Assessments
SOC	System Organ Class
SOP	Standard Operation Practices
SpO ₂	hemoglobin-O ₂ saturation determined by pulse oximetry

TCO2	transcutaneous CO2
THC	9-delta-tetrahydrocannabinol
TTO	time to onset
TV	tidal volume
uL	microliter(s)
ULN	upper limit of normal
US	United States
VAS	visual analog scale
WBC	white blood cell (count)
WHO	World Health Organization

1 Introduction

This statistical analysis plan (SAP) is designed to outline the statistical methods for the [NAL1004](#) study regarding test drug of fentanyl, naloxone, nalmefene and to assess the change in minute ventilation at 5 minutes of intramuscular nalmefene and intranasal naloxone reversal from the opioid induced nadir.

This document has been prepared based on [protocol Amendment 1](#) dated July 28, 2022. Details will be described in this analysis plan to ensure that the data listings, summary tables and figures which will be produced, and the statistical methodologies that will be used, are complete and appropriate to allow valid conclusions regarding the study objectives.

This analysis plan was finalized and approved by the sponsor [REDACTED] prior to the planned database lock.

This SAP supersedes the statistical considerations identified in the protocol; where considerations are substantially different, they will be identified, and justification will be provided. If additional analyses are required to supplement the planned analyses described in the SAP, they may be performed and will be identified in the clinical study report (CSR).

2 Study Design Overview

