2.2 Sample Size Justification

Part 1: A sufficient number of subjects will be screened and entered into Part 1 to provide the number of subjects required in Part 2.

Part 2: A total of up to 22 subjects will be randomized to complete approximately 20.

In a non-inferiority test on MV at 5min from a 4 period, 2 treatment replicate cross-over design, a total sample size of 20 would achieve >90% power at a 2.5% significance level (1-sided) when the true difference between the means is 0.8L/min, the non-inferiority margin is -0.5L/min, and the within-subject standard deviation is 1.2L/min.

In a superiority test on MV at 5min from a 4 period, 2 treatment replicate cross-over design, a total sample size of 20 would achieve 83% power at a 2.5% significance level (1-sided) when the true difference between the means is 0.8L/min and the within-subject standard deviation is 1.2L/min.

The planned sample size is adequate for sequential testing of noninferiority followed by superiority.

3 Study Objectives

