5.3 Eligible Analysis Set (EAS)

Twenty subjects will be expected to complete the study, each of whom will receive nalmefene or naloxone in different order after fentanyl -induced respiratory depression (OIRD).

For each period, eligible analysis set (EAS) include subjects/periods who are randomized, receive study drug, have at least 1 valid PD measurement, and their OIRDs are worse than baseline for MV and TCO₂. Note: baseline and OIRD for MV and TCO₂ may be different. Therefore, eligible analysis set for each PD parameter and period may be different.

To evaluate the treatment difference between nalmefene and naloxone, the same treatment under different periods will be pooled by averaging PD parameters from eligible data for each subject.

This analysis set will be used as primary analysis.

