6.2.1 Multiplicity Adjustment

For the primary endpoint, the non-inferiority test will be performed first. If non-inferiority is achieved, superiority will be tested sequentially. Using this hierarchical test procedure, the comparison of the two treatments will be tested based on a one-sided alpha = 0.025.

The secondary endpoints will not be adjusted for multiplicity.

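### SAP 9.2 names no model for the primary treatment difference; the stated 83% superiority power fits a period-level analysis, while the planned averaging of replicates gives about 81%

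*SAP*

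**What the plan says.** SAP 6.2 sets two ordered hypotheses on the difference in means, with a non-inferiority margin of -0.5 L/min and then zero. SAP 6.2.1 adds that "the comparison of the two treatments will be tested based on a one-sided alpha = 0.025".

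The primary analysis itself is in SAP 9.2: "The change in MV from OIRD at 5 min after administration of antagonist will be provided by treatment in tables and figures", with a 95% confidence interval. It does not name a test, model, period or sequence term, covariate or df method, and it does not say that the interval is for the treatment difference. SAP 7 (efficacy) is marked not applicable.

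SAP 5.3, and 5.4 in the same words, fix how replicates are handled: "the same treatment under different periods will be pooled by averaging PD parameters from eligible data for each subject". SAP 5.3 also expects unequal numbers of usable periods: "Therefore, eligible analysis set for each PD parameter and period may be different".

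SAP 9.1 says that "the following parameters will be calculated to evaluate the action of OIRD for each subject and each period", and one of these parameters is "OIRD value - Median value of the PD data between -10 and -5 minutes before the start of the antagonist".

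SAP 2.2 gives the power statement, "In a superiority test on MV at 5min from a 4 period, 2 treatment replicate cross-over design": 83% with 20 subjects, a true difference of 0.8 L/min and a within-subject SD of 1.2 L/min. SAP 1 states that "This SAP supersedes the statistical considerations identified in the protocol".

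**The concern.** The two tests that decide the trial have no stated estimator, and the parts of the SAP that bear on the choice point in different directions. The power figure fits an analysis of all four periods per subject. The analysis-set sections reduce each subject to one value per treatment, and so to one difference. These analyses have different degrees of freedom and different power, and they respond differently if subjects vary in how they respond to the two products.

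The pre-antagonist OIRD is available in every subject and period and is used only by subtraction. Subtraction fixes its slope at 1. Estimating the slope can reduce residual variance at no cost in data.

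What is at stake is the superiority step: how much power it has, and whether its type I error is protected if the analyst chooses the period-level model that the 83% implies. Bias in the treatment estimate is not at issue.

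**Working it through.** **Inputs from the documents.** N = 20 completers, two replicates per treatment, difference 0.8 L/min, margin -0.5 L/min, within-subject SD 1.2 L/min, one-sided alpha 0.025 (SAP 2.2, 6.2, 6.2.1). **Assumed:** 1.2 L/min is the SD of the change from OIRD.

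**1. Reproduce the 83%.** A subject's difference between two two-replicate means has variance 1.2²/2 + 1.2²/2 = 1.44 when there is no interaction. SE = 1.2/√20 = 0.2683, and the noncentrality is 0.8/0.2683 = 2.98. Power is from the noncentral t.
- Period-level: 80 observations less 1 (mean), 19 (subjects), 3 (periods) and 1 (treatment) leave 56 df. Power is 83.4%, which matches the SAP.
- Averaged: 20 differences give 19 df (80.7%), or 18 df with a sequence term (80.5%).
- Non-inferiority: (0.8 + 0.5)/0.2683 = 4.84, giving 99.7% (56 df) or 99.6% (19 df).

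**2. Allow subjects to differ in response.** Let sD be the between-subject SD of the true treatment difference (not in the documents).
- Averaged analysis, sD = 0.6: SD = √(1.44 + 0.36) = 1.34, superiority power 71.6%, non-inferiority 98.4%.
- One-sided type I error of the 56-df model without an interaction term, simulated with alternating sequences (assumed, since SAP 2.1 gives only periods 1-2): 2.5%, 3.4% and 5.6% at sD = 0, 0.6 and 1.2. Paired averages stay at 2.5-2.6%.

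**3. Effect of adjusting for OIRD.** Let k be the within-subject SD of OIRD divided by that of MV at 5 min, and r their within-subject correlation. Neither is in the documents. The ratio of adjusted to unadjusted residual variance is (1 - r²)/(1 + k² - 2rk):
- k = r = 0.5: 0.75/0.75 = 1.00, so nothing is gained.
- k = 0.75, r = 0.3: 0.91/1.1125 = 0.82.
- k = 1, r = 0.5: 0.75/1 = 0.75.

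Simulated superiority power (%):

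| k, r | sD | averages, unadjusted | averages + averaged OIRD | period-level + OIRD, with interaction term |
|---|---|---|---|---|
| 0.5, 0.5 | 0 | 80.5 | 77.8 (sequence term fitted) | 79.3 |
| 0.75, 0.3 | 0 | 80.5 | 85.8 | 86.8 |
| 1, 0.5 | 0 | 81.0 | 88.5 | 89.4 |
| 0.75, 0.3 | 0.6 | 71.2 | 75.6 | 77.1 |
| 1, 0.5 | 0.6 | 71.5 | 78.3 | 79.7 |

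Most of the gain comes from the covariate; leaving the averages adds about 1 to 2 points. With 10% of periods missing at random (k = 0.75, r = 0.3), the three analyses give 73.7, 78.9 and 80.9% at sD = 0, and 65.6, 69.5 and 70.8% at sD = 0.6. At k = r = 0.5 with missing periods, the period-level model is up to 2.7 points above the averaged one with the covariate.

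These scenarios do not bound the gain. At k = 1, r = 0.3 the averaged analysis with OIRD reaches 92.6%, about 12 points above the unadjusted averages.

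**The case against.** Several stronger readings are tempting, and the documents do not support them.

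- *Averaging makes the period-specific OIRD unusable.* It does not. The endpoint is the change from each period's own OIRD, so OIRD already enters by subtraction before averaging. Averaged OIRD can still serve as a subject-level covariate, and it recovers most of the gain.
- *OIRD adjustment has a known benefit.* It does not, because k and r are not given. With SD 1.2 L/min for the change, the larger gains in the table imply a within-subject OIRD SD of 0.75 × 1.2/√1.1125 = 0.85 up to 1.2 L/min. Fentanyl is titrated towards a common degree of depression (protocol synopsis), which could make the true SD smaller.
- *No model exists anywhere.* That cannot be shown. The protocol text available ends at section 1.3, and the SAP 1 sentence goes on to promise that substantial departures from the protocol will be identified and justified. What can be said is that SAP 9.2 and the protocol synopsis name none.
- *Subjects with one eligible period are weighted like those with two.* That is a natural consequence of simple averaging, but the SAP states no weighting rule.

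It is also fair to say that the difference between 83% and 81% is small, that non-inferiority is hardly touched, and that the exact mixed-model specification is one defensible choice among several. All of this stands. It limits the size of the point, but it does not reconcile SAP 2.2 with SAP 5.3 or supply the missing model.

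**Conclusion.** The point holds as one of specification and efficiency. SAP 9.2 does not say how the treatment difference will be estimated or tested. The 83% in SAP 2.2 belongs to a period-level analysis without interaction, whereas the averaging in SAP 5.3 and 5.4 gives 80.5-80.7%, roughly 3 points less. Non-inferiority power is above 99% at the planning values either way.

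The period-level model implied by the 83% exceeds its nominal 2.5% if response differences between subjects are real. The documents give no value for these, and with an intramuscular product compared with an intranasal one they cannot be excluded.

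Compared with unadjusted averages, a period-level model with OIRD and an interaction term loses about 1 point when r = k, gains about 6 at k = 0.75, r = 0.3 and about 8 at k = 1, r = 0.5, and could gain more. All of these figures rest on 1.2 L/min being the SD of the change. The OIRD adjustment also assumes negligible carry-over from earlier periods into later-period OIRD.

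**What to change.** - **SAP 9.2:** base both hypotheses on the treatment difference and its 95% CI from a model for the change in MV from OIRD at 5 min, with treatment, period, sequence and OIRD as fixed effects. Preferably fit it at period level with random subject and subject-by-treatment terms and small-sample df (Kenward-Roger is one choice).
- **SAP 5.3 and 5.4:** align the averaging rule with that model. If averaging is kept, use averaged OIRD as the covariate and restate the superiority power without the covariate as about 81%.
- **Sensitivity:** keep the unadjusted change.
- **SAP 2.2:** state whether 1.2 L/min is the SD of MV at 5 min or of the change, and whether no subject-by-treatment interaction is assumed. Show any claimed gain from adjustment over a stated range of k and r.

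The cost is text only: OIRD is already derived, the endpoint does not change and no data are added. The statistical price is a loss of about 1 point at period level, or 2 to 3 with averaged data, when r = k. The period-level loss rises to about 3 points if the software bounds the interaction variance at zero. The period-level model has about 18 df, not 56, and the carry-over assumption should be written down.

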9.3 Secondary Endpoint(s) Analysis

Change in MV from opioid induced nadir (Opioid Induced Respiratory Depression (OIRD))

- Pre-specified Time Point: 2.5 min, 10 min, 15 min, 20 min, 90 min after administration of antagonist

The change in MV from OIRD will be provided by treatment in tables and figures with 95% confidence interval presented.

Maximum of Reversal in MV - The highest MV achieved after administration of antagonist

- Time frames: 0-2.5 min, 0-5 min, 0-10 min, 0-15 min, 0-20 min, 0-90 min from administration of antagonist

The maximum reversal on MV (L/min) will be summarized by treatment in tables with 95% confidence interval provided.

Time to Maximum of Reversal in MV - Time from administration of antagonist to Maximum reversal (change in MV)

- Time frames: 0-2.5 min, 0-5 min, 0-10 min, 0-15 min, 0-20 min, 0-90 min from administration of antagonist

The time to maximum reversal on MV (L/min) will be summarized by treatment in tables with 95% confidence interval provided.

To reduce the moment-to-moment variation, additional smoothing windows may be applied to assess the robustness of PD results. For example:

Approach 1: Based on 1-minute window smoothed MV data (Smooth every 1 min of the raw data with center smoothing).

Approach 2: Based on 4-minutes window smoothed MV data (Smooth every 4 mins of the raw data with center smoothing)

9.4 Exploratory Endpoint(s) Analysis

Time to Onset (TTO) - onset of reversal

In the setting of opioid overdose, onset of reversal is expected within minutes following antagonist administration. A 30-minute window was selected to ensure the initial onset is fully captured. If TTO for X% of reversal is not achieved, then it will be considered a reversal failure and will be imputed to 30 minutes.

Onset of reversal for each treatment will include:

- TTO: Time from administration of antagonist (Nalmefene, Narcan) to X% of baseline reversal, where baseline is defined as median value of the PD of interest during the 10 minutes before the start of Fentanyl

Thresholds (X%) of reversal is defined as X% of baseline reversal and calculated as X % * (Baseline – OIRD) + OIRD, where X are 25, 33, 50, 67, 75, 90, and 100. From the onset of reversal from individual periods of each treatment, observed onset of reversal for a pooled period is calculated based on:

- Eligible analysis set - the observed onset of reversal for a pooled treatment period will be the average of onset from eligible periods

Bar charts, scatter plots and overlay boxplots of time to onset of reversal will be plotted by treatment and pooled treatment periods if data warrants.

10 Definitions and Conventions for Data Handling

10.1 Definition of Baseline

For all evaluations unless otherwise noted, baseline is defined as the most recent non-missing measurement prior to or on the first administration of Fentanyl for qualification phase or each period during treatment phase, including unscheduled measurements. Baseline can be the same date as first dose, given the measurement is expected prior to first dose when only date information is available.

10.2 Definition of Study Days

Unless otherwise noted, study days of an evaluation are defined as number of days relative to the first dosing date of Fentanyl of qualification or treatment phase which is designated as Day 1, and the preceding day is Day -1, the day before that is Day -2, etc.

- If evaluation date is on or after first dose date, then study days are calculated as
 - Evaluation date minus - first dose date of study drug + 1
- If evaluation date is before first dose date, then relative study days are calculated as
 - Evaluation date - first dose date of study drug

10.3 First Dose Date of Study Treatment

The date of first dose of study treatment is defined as the earliest dose date of study drugs in the treatment period.

